# 6.3.8 Day 35 (± Days)

The following procedures will be performed on Day 35 ( $\pm 2$  days):

- Perform a neurological examination (all patients) and a symptom-directed physical examination as clinically indicated (ie, new signs or symptoms and follow-up on earlier findings) and measure weight.
- Assess clinical signs and symptoms.
- Record vital signs, including temperature, blood pressure, heart rate, respiratory rate, and oxygen saturation.
- Perform CT scan if clinically indicated.
- Collect samples for fungal cultures (eg, from BAL fluid, sputum, bronchial brush, sinus aspirate, tracheal aspirate) as clinically indicated.
- Collect BAL samples per SOC for culture and CCI testing as clinically indicated.
- Administer 600 mg APX001 by IV infusion over 3 hours QD or 800 mg APX001 PO QD.
- Record concomitant medications.
- Assess adverse events.
- Review accountability for all returned study drug.

# 6.3.9 Day 42 (± Days)

If EOST procedures are performed after Day 39, Day 42 procedures will not be required. The following procedures will be performed on Day 42 ( $\pm 2$  days):

- Administer 600 mg APX001 by IV infusion over 3 hours QD or 800 mg APX001 PO QD.
- Record Investigator assessment of global response.
- Assess survival status.
- Perform urine or serum pregnancy test on women of childbearing potential only.
- Perform a complete physical examination including assessment of general appearance, skin, eyes, heart, chest, abdomen, and a neurological examination and measure weight.

- Assess clinical signs and symptoms.
- Record vital signs, including temperature, blood pressure, heart rate, respiratory rate, and oxygen saturation.
- Perform 12-lead ECG in triplicate.
- Perform clinical laboratory assessments (serum chemistry, hematology [including CBC with differential], coagulation [including PT/INR], and urinalysis).
- Perform CT scan if clinically indicated.
- Collect serum samples for analysis of CCI and C.
- Collect samples for fungal cultures (eg, from BAL fluid, sputum, bronchial brush, sinus aspirate, tracheal aspirate) as clinically indicated.
- Collect BAL samples per SOC for culture and CCI testing as clinically indicated.
- Collect plasma PK samples predose for IV dosing or at any time in clinic for PO dosing.
- Record concomitant medications.
- Assess adverse events.
- Review accountability for all returned study drug.

#### 6.4 End of Study Treatment (+2 Days)

The EOST should occur as soon as possible following completion of APX001 dosing and within 2 days of last dose. The following procedures will be performed at EOST (+2 days):

- Record Investigator assessment of global response.
- Assess survival status.
- Perform urine or serum pregnancy test on women of childbearing potential only.
- Perform a complete physical examination including assessment of general appearance, skin, eyes, heart, chest, abdomen, and a neurological examination and measure weight.
- Assess clinical signs and symptoms.
- Record vital signs, including temperature, blood pressure, heart rate, respiratory rate, and oxygen saturation.
- Perform 12-lead ECG in triplicate.
- Perform clinical laboratory assessments (serum chemistry, hematology [including CBC with differential], coagulation [including PT/INR], and urinalysis).
- Perform CT scan.
- Collect serum samples for analysis of CCI and C
- Collect samples for fungal cultures (eg, from BAL fluid, sputum, bronchial brush, sinus aspirate, tracheal aspirate) as clinically indicated.

- Collect BAL samples per SOC for culture and CCI testing as clinically indicated.
- Collect plasma PK samples at any time in clinic.
- Record concomitant medications.
- Assess adverse events.
- Review accountability for all returned study drug.

#### 6.5 Follow-Up Visit (4 Weeks After End of Study Treatment [±3 Days])

The following procedures will be performed at the Follow-Up Visit (4 weeks after EOST  $[\pm 3 \text{ days}]$ ):

- Perform urine or serum pregnancy test on women of childbearing potential only.
- Perform a neurological examination (all patients) and a symptom-directed physical examination as clinically indicated (ie, new signs or symptoms and follow-up on earlier findings) and measure weight.
- Assess clinical signs and symptoms.
- Record vital signs, including temperature, blood pressure, heart rate, respiratory rate, and oxygen saturation.
- Perform CT scan if clinically indicated.
- Collect samples for fungal cultures (eg, from BAL fluid, sputum, bronchial brush, sinus aspirate, tracheal aspirate) as clinically indicated.
- Collect BAL samples per SOC for culture and CCI testing as clinically indicated.
- Collect serum sample for analysis of C
- Collect plasma PK samples at any time in clinic.
- Record concomitant medications.
- Assess adverse events.

# 6.6 Follow-Up Phone Call (Day 84 [±3 Days])

The Follow-Up Phone Call will occur 12 weeks (±3 days) after Day 1 (Baseline).

The following procedures will be performed during the Follow-Up Phone Call (Day 84 [±3 days]):

• Assess survival status.

#### 6.7 Early Termination Visit and Withdrawal Procedures

For patients who are withdrawn from the study prior to completion, the following procedures will be performed at an E/T Visit:

- Perform urine or serum pregnancy test on women of childbearing potential only.
- Perform a complete physical examination including assessment of general appearance, skin, eyes, heart, chest, abdomen, and a neurological examination and measure weight.
- Assess clinical signs and symptoms.
- Record vital signs, including temperature, blood pressure, heart rate, respiratory rate, and oxygen saturation.
- Perform 12-lead ECG in triplicate.
- Perform clinical laboratory assessments (serum chemistry, hematology [including CBC with differential], coagulation [including PT/INR], and urinalysis).
- Perform CT scan if clinically indicated.
- Collect serum samples for analysis of CCI and C.
- Collect samples for fungal cultures (eg, from BAL fluid, sputum, bronchial brush, sinus aspirate, tracheal aspirate) as clinically indicated.
- Collect BAL samples per SOC for culture and CCI testing as clinically indicated.
- Collect plasma PK samples at any time in clinic.
- Record concomitant medications.
- Assess adverse events.

# 7 EFFICACY ASSESSMENTS

#### 7.1 Primary Efficacy Endpoint

The primary efficacy parameter is the following:

• All-cause mortality through Day 42.

**Note:** All-cause mortality will represent the percentage of patients who die after the first dose of study drug through Day 42 from any cause.

Every attempt must be made to record survival status at Day 42 or anytime thereafter for all dosed patients, regardless of their status of treatment, as long as the patient has not withdrawn consent from participation in the study. An in-person assessment is preferred; however, this assessment may also be performed via a telephone call if an in-person visit is not possible.

#### 7.2 Secondary Efficacy Endpoint

The secondary efficacy parameter is the following:

• Global response at EOST

#### 7.4 Clinical Signs and Symptoms Assessment

Assessment of clinical signs and symptoms will include examination of the following body systems: general appearance including skin, head, eyes, ears, nose, throat, neck, trunk, lymph nodes, respiratory, cardiovascular, gastrointestinal, genitourinary, musculoskeletal, neurological, psychological, lymphatic/hematological, and endocrine/metabolic.

#### 7.5 Microbiological Assessments

#### 7.5.1 Pathogen DNA

Blood samples and/or other diagnostic specimens (eg, BAL) for pathogen DNA analysis utilizing next-generation sequencing (optional) and/or PCR analysis will be collected at Screening. Polymerase chain reaction analysis will be performed at a central laboratory and potentially at the local laboratory. The Sponsor may provide sites with a validated qPCR kit to use for testing locally. Optional next-generation sequencing of pathogen DNA will be performed by Karius.

#### 7.5.2 Aspergillosis Urine Test

A urine sample will be collected at Screening for an MycoMEIA.

#### 7.5.3 Serum Biomarkers

Serum samples for the analysis of CCI will be collected at Screening; predose on Days 1 (Baseline), 2, and 3; on Days 7, 14, 28, and 42; at EOST; and at the E/T Visit (if applicable). Analysis of CCI will be reported at the local laboratory as clinically indicated, and an aliquot of the sample will be sent to the central laboratory for analysis.

Serum samples for analysis of will be collected at Screening; predose on Day 1 (Baseline); on Days 14, 28, and 42; at EOST; at the Follow-Up Visit; and at the E/T Visit (if applicable). Analysis of will be reported at the local laboratory as clinically indicated, and an aliquot of the sample will be sent to the central laboratory for analysis of

#### 7.5.4 Bronchoalveolar Lavage

Bronchoalveolar lavage samples will be collected per SOC for culture at the local laboratory and CCI testing at the central laboratory as clinically indicated at any visit from Screening throughout the study.

#### 7.5.5 Fungal Culture

Samples for fungal cultures (eg, from BAL fluid, sputum, bronchial brush, sinus aspirate, tracheal aspirate) will be collected and processed for culture and susceptibility by the local laboratory at Screening, and as clinically indicated at any visit from Day 1 (Baseline) through EOST, at the Follow-Up Visit, and at the E/T Visit (if applicable). Screening samples for fungal cultures to determine eligibility may have been collected as SOC within 120 hours prior to initial dosing. All fungal isolates cultured at the local laboratory will be sent to the central mycology reference laboratory for confirmation of identification and susceptibility testing.

#### 7.6 Pharmacokinetic Assessments

Plasma samples for PK (APX001 [prodrug] and APX001A [active moiety]) will be collected predose and 3 hours post start of infusion on Days 1 (Baseline), 2, 3, 7, and 14; predose on Days 28 and 42; and at any time in clinic at EOST, the Follow-Up Visit, and the E/T Visit (if applicable). Additionally, for patients who switch to PO dosing, samples should be collected predose and at 3 hours postdose on the initial day of PO dosing, Day 7, and Day 14 and at any time in clinic on Days 28 and 42, at EOST, at the Follow-Up Visit, and at the E/T Visit (if applicable). If the patient switches back to IV dosing, PK samples should be collected predose and at 3 hours post start of infusion on that day as well.

Optionally, if body fluids are sampled as part of routine patient management (eg, BAL, lumbar puncture, paracentesis, vitreal fluid collection, abscess drainage), within approximately 2 hours of blood sampling for PK, these samples may be stored for future analysis of APX001 and APX001A levels.

#### 8 SAFETY ASSESSMENTS

#### 8.1 Adverse Events

An adverse event is defined as any untoward medical occurrence in a clinical investigation patient administered a pharmaceutical product, which does not necessarily have a causal relationship with this treatment. An adverse event can therefore be any unfavorable and/or unintended sign (including an abnormal laboratory finding), symptom, or disease temporally associated with the use of an IMP, whether or not related to the IMP. All adverse events, including observed or volunteered problems, complaints, or symptoms, are to be recorded on the appropriate eCRF.

Adverse events, which include clinical laboratory test variables, will be monitored and documented from the time of initial dosing through the Follow-Up Visit. Patients should be instructed to report any adverse event that they experience to the Investigator, whether or not they think the event is due to study treatment. Following initial dosing, Investigators should make an

assessment for adverse events at each visit and record the event on the appropriate adverse event eCRF.

Wherever possible, a specific disease or syndrome rather than individual associated signs and symptoms should be identified by the Investigator and recorded on the eCRF. However, if an observed or reported sign or symptom is not considered a component of a specific disease or syndrome by the Investigator, it should be recorded as a separate adverse event on the eCRF. Additionally, the condition that led to a medical or surgical procedure (eg, surgery, endoscopy, tooth extraction, or transfusion) should be recorded as an adverse event, not the procedure itself.

Any medical condition already present at initial dosing should be recorded as medical history and not be reported as an adverse event unless the medical condition or signs or symptoms present at Baseline changes in severity, frequency, or seriousness at any time during the study. In this case, it should be reported as an adverse event.

Clinically significant abnormal laboratory or other examination (eg, ECG) findings that are detected during the study or are present at initial dosing and significantly worsen during the study should be reported as adverse events, as described below. The Investigator will exercise his or her medical and scientific judgment in deciding whether an abnormal laboratory finding or other abnormal assessment is clinically significant. Clinically significant abnormal laboratory values occurring during the clinical study will be followed until repeat tests return to normal, stabilize, or are no longer clinically significant. Abnormal test results that are determined to be an error should not be reported as an adverse event. Laboratory abnormalities or other abnormal clinical findings (eg, ECG abnormalities) should be reported as an adverse event if any of the following are applicable:

- If an intervention is required as a result of the abnormality
- If action taken with the study drug is required as a result of the abnormality
- Based on the clinical judgment of the Investigator

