# **1.2.2 Potential Benefits**

APX001 may have potential benefits compared to the current SOC for treatment of invasive infections caused by *Aspergillus* spp. or rare molds. Furthermore, APX001 has a differentiated safety profile, is available as IV and PO formulation, and may have fewer DDIs than the SOC treatments.

Patients with azole-resistant mold infections, including azole-resistant *A. fumigatus* and some rare molds (eg, *Fusarium* spp., *Scedosporium* spp., Mucorales fungi) typically receive IV treatment with a polyene. Polyenes have been associated with risk of nephrotoxicity, electrolyte imbalance, and infusion reactions which can be limiting in patient care. APX001 has broad-spectrum antifungal activity with coverage against azole-resistant molds, and has the potential to be safer and easier to use compared to polyene.

APX001 may provide an advantage over a polyene for the treatment of "breakthrough" infections in patients receiving prophylaxis with mold active triazoles. APX001 has the potential to provide antifungal coverage for *A. fumigatus* and rare molds, without the potential for polyene-induced toxicities. With wide tissue penetration, APX001 may provide a benefit for the treatment of patients with invasive fungal infections in the eye and central nervous system.

APX001 may provide a benefit to patients with invasive fungal infections who are unable to receive treatment with a mold-active azole due to intolerance, toxicity, or clinically significant drug interactions. APX001 has the potential to provide broad-spectrum antifungal coverage, without the risk of hepatic or other azole-associated toxicities, and is expected to be less likely to induce clinically significant drug interactions.

Thus, APX001 is an investigational drug therapy that may fill an unmet need with a unique mechanism of action and no suspected cross-resistance to other mold active antifungals seen in animal models or surveillance to date.

Additionally, in those patients with a COVID-19 pneumonia who develop invasive aspergillosis, APX001 may provide a potential treatment for the secondary IPA infection.

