# 5.5.3 Study Drug Administration

APX001 for IV administration will be delivered via central venous catheter (CVC) or peripheral IV line access according to SOC. APX001 for IV administration must not be infused into the same CVC or peripheral line access that is being used concurrently for the administration of other medications. Volumetric infusion pumps will be used during the administration of APX001 to ensure the prescribed volume is delivered to the patient. The infusion rate and total volume administered will be recorded on the patient's IV bag label and in their source documentation.

A loading dose of 1000 mg APX001 will be administered over 3 hours by IV infusion BID within the first 24 hours after initiation of the first infusion. On Days 2 and 3, 600 mg APX001 will be administered over 3 hours by IV infusion QD. From Day 4 through EOST, the IV dose remains 600 mg APX001 administered over 3 hours by IV infusion QD, or patients may be switched to PO administration of 800 mg APX001 QD.

Patients who have completed a minimum of 3 days of IV APX001 may be switched from IV to PO APX001 if they are able to ingest medication PO and the Investigator deems it is in the patient's best interest to do so. The switch to PO can be done on any day from Day 4 onwards. Patients will remain hospitalized for at least 2 days following the initial switch from IV to PO so that their tolerance to the oral medication may be evaluated and treated as necessary. Oral APX001 may be given with food, and prophylactic antiemetics may be administered. Patients may be switched between IV and PO as needed. Oral APX001 may be given as an outpatient.

Study drug will not be administered for longer than 6 weeks (inclusive of the loading dose [Day 1]). If an Investigator documents an improvement or resolution in clinical signs and symptoms prior to 6 weeks, eg, if follow-up imaging (as applicable) shows improvement; or a mycological response (if amenable to repeat sampling) is observed, the Investigator may choose to discontinue dosing. Patients will be requested to return for an EOST and Follow-Up Visit and to agree to a Follow-Up Phone Call. Patients who still require treatment after EOST should continue on OLAT.

Tablets are to be administered at the same time each day, whole, and taken by mouth with water. No splitting or crushing of tablets is allowed.

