#### 9.2.2 Analysis of Safety

All safety analyses will be performed on the Safety Population. Safety data will be subject to clinical review and summarized by appropriate descriptive statistics. A DSMB will be assigned to monitor safety on an ongoing basis throughout the study.

Analyses will be based on adverse events, vital signs, clinical laboratory assessments, and ECGs. Safety analyses will be descriptive and will be presented in tabular format with the appropriate summary statistics.

A TEAE is defined as an adverse event that started on or after the administration of study drug. The number and percentage of patients with TEAEs will be tabulated by system organ class, preferred term, and by severity and relationship to treatment. Serious adverse events and adverse events leading to discontinuation from study drug will be summarized. Listings will also be provided for SAEs and adverse events leading to discontinuation of study drug.

Descriptive statistics will be provided for clinical laboratory, vital sign, and ECG interval data for both actual values and changes from Baseline over time.

Abnormal physical examination findings will be listed.

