3.7. Adverse Events

An adverse event is defined as any untoward medical occurrence in a clinical investigation patient administered a pharmaceutical product, which does not necessarily have a causal relationship with this treatment. An adverse event can therefore be any unfavorable and/or unintended sign (including an abnormal laboratory finding), symptom, or disease temporally associated with the use of an IMP, whether or not related to the IMP. Any adverse event that started on or after the administration of study drug will be considered a treatment emergent adverse event (TEAE). AEs will be captured from the time of initial dosing through the Follow-Up Visit. Events that occur after Day 42 (maximum duration of treatment with fosmanogepix) but prior to and including the Follow-Up visit will be considered treatment

emergent. All AEs will be coded to system organ class (SOC) and preferred term (PT) using the MedDRA.

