6.8.8. Adverse Events

An overview of AEs will be provided including counts and percentages of patients (and event counts) with the following:

- Any AEs.
- Any TEAEs (overall and by maximum severity).
- Any study drug related TEAEs (overall and by maximum severity).
- Any serious AEs (SAEs).
- Any treatment-emergent SAEs (TESAEs).
- Any TRSAEs).
- Any TEAEs leading to discontinuation of study drug.
- Any TRAEs leading to discontinuation of study drug.
- Any AEs leading to death.

The number and percentage of patients who experienced at least one TEAE will be presented by SOC and PT. TEAEs, TRAEs, study drug withdrawals due to TEAEs and TRAEs, and all SAEs will be summarized in the same manner.

Summaries will be provided by worst grade for the number and percentage of patients with TEAEs and TRAEs by SOC and PT.

Although a patient may have two or more TEAEs, the patient is counted only once within a SOC and PT category. The same patient may contribute to two or more PTs in the same SOC category.

A list of patients who have SAEs, a list of patients who discontinue from study drug due to TEAEs or TRAEs, and a list of death due to AEs will be provided. All AEs will be listed.

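### The adverse event tables do not separate onset on APX001 from onset after it, so all-causality TEAE, SAE and death counts mix the study drug period with the next antifungal

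*Protocol*

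**What the plan says.** Protocol section 8.1 sets the collection period: "Adverse events, which include clinical laboratory test variables, will be monitored and documented from the time of initial dosing through the Follow-Up Visit". The counting rule is elsewhere. Protocol section 9.2.2 reads: "A TEAE is defined as an adverse event that started on or after the administration of study drug", with no end date. SAP section 3.7 repeats the definition and extends it explicitly: "Events that occur after Day 42 (maximum duration of treatment with fosmanogepix) but prior to and including the Follow-Up visit will be considered treatment" emergent.

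The end-of-treatment (EOST) visit is due within 2 days of the last dose (Protocol section 6.4), and the Follow-Up Visit 4 weeks ±3 days after EOST (section 6.5). Dosing lasts at most 6 weeks and may stop earlier. On what follows, Protocol section 5.5.3 says: "Patients who still require treatment after EOST should continue on OLAT".

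SAP section 6.8.8 summarises events by system organ class and preferred term (SOC/PT), worst grade, relatedness, seriousness, drug discontinuation and death. No summary is split by onset before or after the last dose, censored at the start of OLAT, or adjusted for exposure. SAP section 6.8.6 tabulates OLAT as a medication category but does not link it to adverse events. (The protocol calls the drug APX001; the SAP calls it fosmanogepix.)

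**The concern.** Safety is part of the primary objective and the study is non-comparative, so the all-causality TEAE table is the main description of what happened to patients on this drug. A control arm would show the background level of events, including those from later antifungals. Here nothing does.

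The move to another antifungal is a planned path, not a rare accident. The patients who take it were enrolled because standard options were limited by resistance, contraindication, intolerance or lack of response (inclusion criterion 3). The protocol itself describes toxicity for one class they might receive: "Polyenes have been associated with risk of nephrotoxicity, electrolyte imbalance, and infusion reactions which can be limiting in patient care". An event that begins two weeks into such a drug is an APX001 TEAE under the current definition, and the planned summary tables give no way to see that it began off APX001.

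**Working it through.** The plan states no figure for the off-drug part of the event window, so there is nothing to reproduce. The check has four steps.

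**1. Length of the off-drug period.** Inputs: last dose to EOST, 0 to 2 days (Protocol section 6.4); EOST to Follow-Up, 28 ±3 days (section 6.5). Days from last dose to Follow-Up, F:
- minimum 0 + 25 = 25
- nominal 0 + 28 = 28
- maximum 2 + 31 = 33

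**2. Off-drug share of the event window.** With T days on drug, share = F/(T + F), for patients who reach the Follow-Up Visit:

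| Last dose | F = 25 | F = 28 | F = 33 |
|---|---|---|---|
| Day 42 | 25/67 = 37% | 28/70 = 40% | 33/75 = 44% |
| Day 28 | 25/53 = 47% | 28/56 = 50% | 33/61 = 54% |
| Day 14 | 25/39 = 64% | 28/42 = 67% | 33/47 = 70% |

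These are shares of calendar time, not of events. The Day 14 row also shows why Day 42, the marker in SAP section 3.7, cannot serve as the dividing line: a patient who stops on Day 14 has Follow-Up at Day 39 to 47, nominally Day 42, so the whole nominal off-drug period would sit before the line.

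**3. What this could do to an event rate.** Let p_on be the risk of a given event on drug, s the share of patients moved to OLAT, and p_off the risk of that event on OLAT before Follow-Up. Assume independence and no new off-drug events in patients without OLAT. A patient counts once per term (SAP section 6.8.8), so

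reported risk = 1 − (1 − p_on)(1 − s × p_off).

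None of the three inputs is in the documents. With assumed values p_on = 10%, s = 25% to 75% and p_off = 5% to 20%:
- low: 1 − 0.90 × (1 − 0.25 × 0.05) = 1 − 0.90 × 0.9875 = 11.1%
- high: 1 − 0.90 × (1 − 0.75 × 0.20) = 1 − 0.90 × 0.85 = 23.5%

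That is 1.1 to 13.5 points, or 0.45 to 5.4 patients out of the 40 planned for Cohort A. The range is too wide to serve as an estimate; it shows only that the effect could be negligible or visible.

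**4. Which outputs are exposed.**
- *Exposed:* all-causality TEAEs (overview, SOC/PT, worst grade), SAEs, and events leading to death.
- *Partly protected:* treatment-related tables, through the investigator's yes/no call.
- *Essentially on-drug already:* TEAEs leading to discontinuation of study drug.
- *Little affected:* scheduled laboratory and ECG summaries, since neither is scheduled at Follow-Up (SAP sections 3.8 and 3.10). One exception: Protocol section 6.3.9 waives Day 42 procedures only if EOST came after Day 39, so an early stopper may have off-drug Day 42 tests.

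**The case against.** The strongest reply is that this is ordinary practice. A follow-up of about 4 weeks for TEAEs is conventional and catches delayed effects; the protocol names liver toxicity as a potential risk (section 1.2.1), which argues against cutting off at the last dose. An all-causality table is not a causal rate: it already contains events from malignancy, chemotherapy and concomitant drugs. All of this stands. A reader might infer that the window is too long; the documents do not support that.

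The relatedness call also does real work. Protocol section 8.1.3 tells the investigator to consider the patient's other drugs, and the treatment-related tables follow from that. The filter is incomplete, though. Under that section a No requires a time course that rules out causality, while a Yes requires that no other cause can be identified. An event with a plausible time course and OLAT as a rival cause fits neither, and section 8.1.1 counts a relationship that cannot be ruled out as a drug reaction.

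Three stronger readings fail:
- *That 37–70% of TEAEs belong to the next drug.* These are shares of time. Some early stoppers stop because they improved and may need no OLAT.
- *That a specific inflation can be quoted.* Multiplying a guessed OLAT share of 30–70% by a guessed event risk of 10–30% gives 3 to 21 points, but neither range is in the documents, and the product counts again patients who already had the event on drug.
- *That renal or electrolyte rates are the main casualty.* The toxicity statement concerns polyenes, while OLAT is any licensed antifungal. After a full course, no chemistry is scheduled beyond EOST, so such events would surface only through clinically prompted tests.

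It is also fair that no safety comparison by treatment duration is planned, and that all events and medications are listed by patient. The information exists; the summary does not use it.

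**Conclusion.** The point holds as a gap in presentation, not an error in the window. Every event up to 25–33 days after the last dose is a TEAE, patients who still need therapy change antifungal inside that period, there is no control arm, and no planned summary shows which TEAEs, SAEs or deaths began on APX001. The off-drug part is 37–44% of the event window for a 42-day course and more for shorter ones, assuming the visit windows are kept and the patient reaches Follow-Up. The effect on event rates cannot be determined from the documents, because the OLAT share and its event rates are not given. The Day 42 mortality endpoint is unaffected. The change is worth making because it is cheap and safety is part of the primary objective.

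**What to change.** In SAP sections 3.7 and 6.8.8:
- Keep the present all-TEAE column as the total.
- Add two columns by onset: on-treatment (first dose to last dose plus a short lag that the sponsor pre-specifies and justifies from the drug's pharmacokinetics) and post-treatment (after that to Follow-Up). Neither document gives a half-life, so the lag cannot be set from them.
- Key the split to each patient's own last dose, not to Day 42.
- Apply it to the overview and the SOC/PT, worst-grade, SAE and death summaries.
- In the post-treatment column, flag events that start on or after the first OLAT dose. Use recorded medication start dates (Protocol section 5.6.3), because SAP section 6.8.6 describes OLAT only as treatment after 6 weeks of study drug, whereas patients may stop sooner.
- State how partial onset dates are assigned, in line with the conservative rule in SAP section 5.4.

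The cost is SAP wording and extra columns; no new data are needed. Late APX001 effects may fall in the post-treatment column, which is why the total stays. The split does not adjust for differing time on drug.
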